7.2 Study Procedures

- Physical and Psychological Screening Procedures: The screening will include:
 - 12-lead electrocardiogram (EKG)
 - Urine pregnancy test if female with childbearing potential
 - Psychiatric assessment including: the M.I.N.I International Neuropsychiatric Interview (M.I.N.I. 7.0.2), Form 90-Drug Inventory (Form 90-DI), Hamilton Depression scale (HAM-D), State-Trait Anxiety Inventory (STAI-Y1), and Columbia Suicide Severity Rating Scale (C-SSRS)

The C-SSRS will be administrated by appropriately trained personnel. All C-SSRS scores will be reported to the Caron Treatment Center Medical Director of Research and the Director of Research. At risk participants will be immediately reported to the Directors of Research. Any participant that reports recent suicidal ideation or behavior on the screening C-SSRS will be referred for further immediate evaluation by a clinician. Clinical judgement and additional consult with the Caron Medical Director, study PI, and/or study staff will be used to further clarify if the subject is eligible to continue in the study. Participants not at risk will be reported weekly.

The Directors will refer the clinical decision to the psychology and medical team. If the patient is deemed to be suicidal, and is willing to get help, the psychology staff will utilize their typical protocol and resources to find placement in a local psychiatric facility (e.g., Philhaven, Lancaster Behavioral Health). The patient may be transported via ambulance or via Caron transportation (depending on how safe staff feels it is to transfer) to the facility for admission. In the case that the participant is uncooperative, Service Access and Management, Inc. (SAM) will be notified to assist with emergency planning. Any participant who develops active suicidal ideation with some intent to act with or without a specific plan will be discontinued from study treatment.

• **Body Weight:** Body weight will be measured daily throughout the study (Days 1-21 [Days 1-33 for 5-dose intervention]).

Blood glucose:

- Blood samples to assess changes in more long-term indices of glycemic control, such as hemoglobin A1c (HbA_{1c}) and fructosamine, will be collected prior to the first dose of study drug (Day 2) and at the end of the target dose (Day 19 [and additionally at Day 31 for 5-dose intervention]). Samples will be analyzed by Caron's clinical laboratory.
- Cardiorespiratory Function: Recordings will be collected using a portable cardiovascular autonomic cart at CaronTC. The data will be recorded via a data acquisition system (PowerLab, ADInstruments). After instrumentation, participants will rest for 10 minutes, followed by 15 minutes of continuous recordings of cardiorespiratory parameters.
 - Blood pressure, heart rate, and respiratory rate will be measured at baseline (Day 1), during study drug administration (Days 2, 8, 14, 19, 20, 26, and 31), and at the end of rebound follow-up (Day 21 [Day 33 for 5-dose intervention]). At each of these time points, participants will be placed in the supine position.
 - Blood pressure will be measured continuously using the finger volume clamp method (NOVA Finapres Medical Systems or similar) and intermittently by an oscillometric brachial artery cuff (Philips SureSigns VS3 or similar).
 - A 3-lead EKG will be used to continuously measure heart rate (Cardiocap/5 GE Healthcare or similar).
 - Respiratory rate will be measured using a pneumography belt, and oxygen saturation by pulse oximeter applied to the finger (BCI 3301 or similar).
- Cue-elicited drug craving will be evaluated. This will be evaluated using Visual Analog Scales (VAS) on Day 1 and Day 19 [and additionally at Day 31 for 5-dose intervention].
 - Cue-elicited craving will be measured on a 0-100 point VAS, where 0= no craving, 100 = maximum craving. Assessments will be taken prior to, and immediately after, exposure to visual drug cues in the Cue Response Task.
- Ecological Momentary Assessment (EMA): EMA data will be collected throughout the study (Days 1-21 [Days 1-33 for 5-dose intervention]) 4 times per day via smartphones for the first 3 days (Days 1-3) and then on a rotating "4-days on, 2-days off" schedule starting Day 6. Data to be collected include: Ambient Drug Craving; Positive and Negative Mood; Pain/Discomfort; and Sleep on 0-100 point VAS.

The smartphones that will be used for EMA data collection will have an app (the Wear-IT app) that will be put on the study smartphone provided to the participant while they are in the study. This smartphone will have a security application installed that prevents user access to all other applications that are not associated with data collection. Smartphones will not be activated on a cellular network resulting in the disabling of voice, text, and internet functions. Research staff will use brief in-person meetings (every other day) as a means to ensure devices are being charged, build rapport, answer participant questions, monitor compliance, and to manually download data for backup storage for upload to a secure server, Virtual COLO, at University Park in State College. Participants will need to plug the phone in to charge each night.

 Physiological Wearables: A "wearable" wristband will be worn throughout the study (Days 1-21 [Days 1-33 for 5-dose intervention]) to monitor stress responses, including acute

changes that may be associated with the drug delivery via injection. Data collected include heart rate, actigraphy for sleep and activity measurement, and stress responses (including acute changes in these measures that may be associated with the drug delivery via injection). A body temperature compliance sensor will be used to validate that the device is being worn. So that participants do not have to charge the actigraphy wristband themselves, participants will have up to two actigraphy wristbands assigned to them, and they will be charged or, if necessary, swapped out at their check-in sessions. Participants may wear the actigraphy wristband while showering or swimming if they wish.

- Neurophysiology Lab Day Measures: Participants will be tested at baseline (Day 1) and at the end of the target dose (Day 19 [and additionally Day 31 for 5-dose intervention]) for cortical activity using Functional Near Infrared Spectroscopy (fNIRS) and VAS during:
 - Visual cue reactivity task to: (a) opioid cues; (b) non-opioid control cues; (c) natural reward cues (e.g., pleasant pictures of food, puppies, positive relationships, etc.) and (d) emotionally neutral stimuli (e.g., images of household objects)
 - The VAS measure of craving pre-post visual cue reactivity task
 - Balloon Analogue Risk Task (BART)

fNIRs data files will be placed into the REDCap database, with access to these files provided to key investigators at Drexel University for signal processing and return for data analyses. These data will be de-identified and will consist only of the unique study id number, raw data, stimulus markers, and date/time stamps that have been modified so that they do not contain the actual visit date.

- **Study drug/placebo administration:** Participants will be taught self-administration by study/nursing staff.
 - All self-administrations will occur via blinded, multi-dose subcutaneous injection pens, and will be observed by nursing staff at CaronTC.
 - Participants will receive medications daily at a specified time (prior to breakfast) throughout the study, starting on Day 2.
 - Participants will be taught to inject the solutions subcutaneously in the abdomen, thigh, or upper arm, and will administer daily injections under the supervision of a study nurse or staff member.
 - Participants will be taught by study staff nurses to attach the needle, check the drug/vehicle flow, select the dose, inject the dose, remove the needle, and dispose of the needle.
 - o Participants will always use a new needle for each dose administration in the study.
- Adverse Events: Adverse events will be monitored continuously throughout the study (Days 1-21 [Days 1-33 for 5-dose intervention]), and at 30 days post-intervention (Day 49 [Day 61 for 5-dose intervention]).

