blood glucose, along with positive effects on body weight, blood pressure, and cholesterol [10]. Furthermore, neuroimaging studies have shown that GLP-1R agonists reduce brain responses to food cues in obese and T2DM participants, but not in lean participants. Specifically, Van Bloemendaal et al. [39] demonstrated that the GLP-1R agonist exenatide (relative to placebo) decreased functional magnetic resonance imaging (fMRI) measures of brain activation in the amygdala, insula, putamen, and, importantly, orbitofrontal cortex (OFC) in response to a series of food related cues (i.e., food vs nonfood pictures) in subjects with obesity and T2DM. This effect was not observed in lean control subjects. The most common side effects of GLP-1R treatment are nausea and diarrhea; less common is injection-site bruising or "reactions" (i.e. erythema, pruritus, and rash) [36]. One meta-analysis found evidence of a slight increase in heart rate, a modest reduction in blood pressure, and no association with hypertension across 60 trials employing 14 different GLP-1R formulations [40]. Further work reported decreased cardiovascular risk [41] and a reduction in major adverse cardiac events including nonfatal stroke, nonfatal myocardial infarction, and cardiovascular mortality [42] in T2DM patients treated with GLP-1R agonists compared with placebo.

All GLP-1R agonists are not the same with regard to treatment of obesity or T2DM. Ex-4 (exenatide) is a short acting GLP-1R agonist with a half-life of 2.4 h in humans [43]. Liraglutide has a longer half-life of about 13 h in humans [44] and, as such, has been found useful as a once/day sc injectable formulation for the treatment of obesity [27, 45] and T2DM [46, 47]. A meta-analysis determined no cause for concern regarding neuropsychiatric safety associated with liraglutide [48].

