3.3 Early Withdrawal of Subjects

3.3.1 Criteria for removal from study

Blood pressure, heart rate, and respiratory rate will be measured on Days 1, 2, 8, 14, 19, and 21. On each day, each measure will be recorded 3-4 times and then averaged. Participants will be withdrawn if they experience an average daily value for any measure on Day 1, 2, 8, 14, or 19:

- Systolic blood pressure (SBP) changes >40 mmHg, or SBP <90 mmHg or >200 mmHg, or clinical symptoms of hypertension (e.g. headache, dizziness, blurred vision, nausea edema) or hypotension (e.g. dizziness, nausea, fainting) develop
- Heart rate reaches levels <40 beats/min or >120 beats/min
- Respiratory rate changes by >5 breaths/minute or reaches levels <10 breaths/minute or >24 breaths/minute

The investigators will also exercise discretion to end an individual's study participation if they should engage in behavior that could jeopardize their own health and well-being or that of others

Participants who develop any new conditions described in the exclusion criteria during the treatment phase of clinical trial will be removed from the study

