7.2.5 Study Test Day – (Day 19)

The following **research-only** measures, all completed on Day 1, will be repeated on Day 19, regardless of intervention length (i.e., 3-dose and 5-dose interventions). Day 19 will serve as the final dose (1.8 mg) day for participants in the 3-dose intervention. For participants in the 5-dose intervention, Day 19 will be the final day at the 1.8 mg dose before moving on to the 2.4 mg dose on Day 20.

- Cardiorespiratory function will be assessed via measurement of blood pressure, heart rate, and respiratory rate as described in Section 7.2.
- Blood samples will be collected for safety laboratory tests (CBC, CMP) and for monitoring of glycemic control. Approximately 4 teaspoons of blood will be collected.
- Body weight data will be collected.

- Cue-elicited drug craving will be evaluated using VAS.
- Neurophysiology measurements will be evaluated using fNIRS during: (1) Visual cue reactivity and (2) BART.
- Collection of ambient drug craving, mood, and sleep data by EMA.
- Stress response, sleep, and activity measurements will be collected via actigraphy wristband.
- C-SSRS
- Urine pregnancy test (if applicable)
- Aes and concomitant medications will be documented.

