7.4.6.5 Prior and Concomitant Therapy

A concomitant therapy is any medication which is administered between study enrollment and the end of the study drug treatment phase. All concomitant therapies will be monitored daily and recorded at minimum

once weekly by study team members during the duration of the treatment phase with the study drug.

The subjects recruited will be current patients in a residential facility for the treatment of opioid dependence. Since the physicians at Caron will be approving patient eligibility, they will know current and past patient medication regimes. Subjects may be taking concomitant medicines/therapies for various reasons at the treatment center. The pharmacy staff at Caron will also know which medications may not be permitted to take with the medication during the study, due to potential counteracting affects.

Precautions: Saxenda is contraindicated with the use of insulin or any other GLP-1R agonist; the use of these medications are identified in the exclusion criteria.

Respiration and heart rate will be monitored at baseline and following all dosage increases.

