9.0 Data and Safety Monitoring Plan

9.1 Periodic evaluation of data

To monitor safety throughout the course of the study, every effort will be made to remain alert to possible Aes/SAEs. If an AE/SAE occurs, the first concern should be for the safety of the subject; CaronTC's medical staff is available 24/7 and will be immediately alerted in the event of a SAE. If necessary, appropriate medical intervention will be provided. At the signing of the written consent form, each subject will have been given the names and telephone numbers of study site staff for reporting Aes/SAEs and medical emergencies.

In this study, any AE/SAE experienced by the subject between the time of first dose of study treatment and 24 hours after the last dose will be recorded on the case report form, regardless of the severity of the event or its relationship to study treatment. During study treatment, the research team will assess the subject for Aes and will record any new Aes/SAEs or updates to previously reported Aes on the electronic case report form.

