10.0 Risks

The following risks are associated with the GLP-1R agonist liraglutide during study treatment

Potential risks associated with the study drug: There is a potential risk of experiencing side effects from the investigational drug. Common side effects of liraglutide include: nausea, diarrhea, vomiting, and decreased appetite. These side effects dissipate over time and are minimized with appropriate dose titration. Other potential side effects, though expected to be rare, include: hypoglycemia, constipation, headache, dyspepsia, fatigue, dizziness, abdominal pain, increased lipase, and vaso-vagal response if there is a history of vaso-vagal response. Serious side effects include: risk of thyroid c-cell tumors, acute pancreatitis, acute gallbladder disease, risk of hypoglycemia with concomitant use of anti-diabetic therapy, heart rate increase, renal impairment, and

suicidal behavior and thoughts. There is also potential risk of irritation at the injection site, and increased drug craving in response to needle use.

An allergic reaction to liraglutide can include hives; fast heartbeat, dizziness, trouble breathing or swallowing, and swelling of face, lips, tongue, or throat. There is also potential risk of irritation at the injection site, and increased drug craving in response to needle use. The side effects of acute withdrawal from liraglutide include nausea and vomiting. With a half-life of 13 hours, liraglutide should be completely eliminated in 65 hours, within the 4-day rebound follow-up observation period. Since liraglutide has not been previously used in patients with OUD, it is considered an investigational drug. Since this drug has not been previously given in OUD, there may be risks that are not known at this time.

Overdose of the study drug, according to the literature, is limited to severe nausea and vomiting and occasional abdominal pain and diarrhea. None of the reported cases resulted in hypoglycemia.

Hypoglycemia signs and symptoms

- Feeling shaky
- Being nervous or anxious
- Sweating, chills and clamminess
- Irritability or impatience
- Confusion
- Fast heartbeat
- Feeling lightheaded or dizzy
- Hunger
- Nausea
- Color draining from the skin (pallor)
- Feeling Sleepy
- Feeling weak or having no energy
- Blurred/impaired vision
- Tingling or numbness in the lips, tongue, or cheeks
- Headaches
- Coordination problems, clumsiness
- Difficulty concentrating
- Slurred speech
- Nightmares or crying out during sleep
- Seizures

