18.5 Reporting Adverse Reactions and Unanticipated Problems to the Responsible IRB

In accordance with applicable policies of The Pennsylvania State University Institutional Review Board (IRB), the investigator will report, to the IRB, any observed or reported harm (adverse event) experienced by a subject or other individual, which in the opinion of the investigator is determined to be (1) unexpected; and (2) possibly or probably related to the research procedures. Harms (adverse events) will be submitted to the IRB in accordance with the IRB policies and procedures.

In the event of an SAE or life-threatening adverse reaction, Caron medical staff will be immediately informed and address the situation. [name] and the medical monitor will be contacted within 12

hours. SAEs will be reported to the DSMB within 24 hours, and to the IRB within 10 days, of the PI's notification of the event. The need to suspend or modify the study procedures will be assessed with the IRB and DSMB. All non-serious Aes will be summarized and included in regular reports to the IRB and DSMB.

Reporting Adverse Reactions and Unanticipated Problems to NIDA

SAEs will be systematically evaluated at each clinic visit. Any SAE, whether or not related to study medication, will be reported to NIDA. SAEs that are "unexpected" and "possibly or probably related" to the research procedures will be reported to the IRB. The clinical PI, [name], will report any SAEs to NIDA within 72 hours of first becoming aware of the event. The initial SAE report will be followed by submission of a completed SAE report to NIDA. All SAEs will be followed until satisfactory resolution or until the site investigator deems the event to be chronic or the participant is stable.

Reporting of IRB actions to NIDA

Any actions recommended by the IRB will be reported to NIDA within 5 calendar days of the PI's notification.

Report of Changes or Amendments to the Protocol

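### Treatment must stop for suicidal ideation with intent, but the first on-treatment C-SSRS is Day 19, after 17 or 18 of the 18 doses in the 3-dose course; add it on Days 8 and 14 (and Day 26 for extenders)

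*Combined protocol and SAP*

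**What the plan says.** Section 7.2 Study Procedures contains the rule: "Any participant who develops active suicidal ideation with some intent to act with or without a specific plan will be discontinued from study treatment". Section 10.0 Risks counts suicidality among the serious side effects of the drug; that list ends, and the next sentence begins, with "suicidal behavior and thoughts. There is also potential risk of irritation at the injection site". The same section says the drug has not previously been given in this population.

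The C-SSRS is scheduled on Day 1 (7.2.1), Day 19 (7.2.5) and, for the 5-dose course only, Day 31 (7.2.9). Both Schedule of Study Activities tables agree. It is absent from the activity lists for Days 2-18 (7.2.2 to 7.2.4) and Days 20-30 (7.2.6 to 7.2.8). The M.I.N.I., HAM-D and STAI-Y1 are Day 1 only. On timing, 7.2.5 says: "Day 19 will serve as the final dose (1.8 mg) day for participants in the 3-dose intervention".

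The vital-sign withdrawal limits have their own measurement schedule. Section 3.3.1 says: "Blood pressure, heart rate, and respiratory rate will be measured on Days 1, 2, 8, 14, 19, and 21", and 18.7 repeats it. Section 7.4.6.5 adds: "Respiration and heart rate will be monitored at baseline and following all dosage increases". For extenders, 7.2 also places cardiorespiratory visits on Days 20 and 26.

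General safety surveillance is described in 9.1, "During study treatment, the research team will assess the subject for Aes", and in 18.5, "SAEs will be systematically evaluated at each clinic visit".

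**The concern.** A stop rule protects participants only if the event is found while there is treatment left to stop. In the 3-dose course, which every participant enters, the one scheduled instrument designed to find this event falls on the last dosing day. Until then the rule depends on ideation being volunteered or noticed during contacts that are not described as asking about it.

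Two features of the plan add to this. Exclusion 14 in Section 3.2 lets a clinician clear a patient with ideation in the past month or an attempt in the past year, so some participants may start at higher risk and then have no structured reassessment for 17 on-drug days. Under 3.3.3, those who stop medication also stop study tasks, and no C-SSRS is scheduled at the follow-up call. Anyone who leaves before Day 19 therefore has no post-baseline C-SSRS. Section 8.2 allows for 20% attrition, which is 0.20 × 50 = 10 participants; the plan does not say when they are expected to leave.

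**Working it through.** **Inputs.** One injection a day before breakfast: Days 2-7 (0.6 mg, 7.2.2), 8-13 (1.2 mg, 7.2.3) and 14-19 (1.8 mg, 7.2.4). For extenders, also Days 20-25 (2.4 mg, 7.2.6 and 7.2.7) and 26-31 (3.0 mg, 7.2.8). On-treatment C-SSRS: Day 19, and Day 31 for extenders. Existing cardiorespiratory visits include Days 8, 14 and 26.

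**Course length.** 6 + 6 + 6 = 18 doses, and 18 + 6 + 6 = 30. Both reproduce the 18-day and 30-day titrations stated in 1.1.

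**Doses still stoppable.** The first dose is on Day 2. A check on Day d therefore follows d − 2 doses if done before that day's injection and d − 1 if done after. With N doses in the course, N − (d − 2) or N − (d − 1) remain. The plan does not state the order of C-SSRS and injection, so both are shown.

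| Course | Check day | Left if before dose | Left if after dose | Status |
|---|---|---|---|---|
| 3-dose, N = 18 | 8 | 18 − 6 = 12 | 18 − 7 = 11 | proposed |
| | 14 | 18 − 12 = 6 | 18 − 13 = 5 | proposed |
| | 19 | 18 − 17 = 1 | 18 − 18 = 0 | current |
| 5-dose, N = 30 | 19 | 30 − 17 = 13 | 30 − 18 = 12 | current |
| | 26 | 30 − 24 = 6 | 30 − 25 = 5 | proposed |
| | 31 | 30 − 29 = 1 | 30 − 30 = 0 | current |

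At the Day 19 check a 3-dose participant has had 17/18 = 94% or 18/18 = 100% of the course.

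**On-drug days with no C-SSRS.**
- Now: Days 2-18 = 17 days; for extenders also Days 20-30 = 11 days.
- With Days 8, 14 and 26 added: Days 2-7 = 6, 9-13 = 5, 15-18 = 4, 20-25 = 6 and 27-30 = 4 days.

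**Comparison with the vital-sign limits.** These are checked on Days 2, 8 and 14 before Day 19. The suicidality rule has no scheduled check in that interval.

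**Extra administrations.** Two per 3-dose participant and three per extender: 50 × 2 = 100 if nobody extends, 50 × 3 = 150 if everybody does. Attrition would lower both figures.

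**The case against.** The strongest reply is that the stop rule is not tied to the C-SSRS and can act on any day. Participants are inpatients receiving counseling. They are seen daily for observed dosing and every other day by research staff, are assessed for adverse events, and have medical cover around the clock (15.4) and a psychiatric referral pathway (7.2). They also rate mood four times a day on EMA days. A research protocol need not describe the facility's routine psychiatric care. Sections 3.3.1 and 18.7 also remove anyone who develops a new condition on the exclusion list, which includes recent ideation. All of this is true, and it lowers the risk. But the broader removal rule also needs ideation to be detected. The every-other-day meetings are described in terms of devices, rapport, questions, compliance and data download. The EMA items listed in 7.2 include none on suicidality, and no real-time review is described. The line in 7.2 on weekly reporting of participants not judged at risk concerns how scores are passed on; it does not schedule a weekly C-SSRS.

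A second reply is that risk appears low. Section 2.2 says: "A meta-analysis determined no cause for concern regarding neuropsychiatric safety associated with liraglutide", and 7.4.1 describes the drug as judged safe in people with a substance use history. This stands. Doses still stoppable is schedule arithmetic and not an estimate of benefit: the documents give no event rate, and only about 25 participants will receive active drug. The C-SSRS itself also depends on honest disclosure. Nothing in the documents links suicidality to dose steps, so the vital-sign comparison shows only that the visits exist.

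A third reply is practical. Section 23.0 puts morning medication at 6:15 to 6:50am, so a check before the dose may not fit the visit. The figures of 11 and 5 may then be the realistic ones.

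**Conclusion.** The concern holds. In the 3-dose course the first on-treatment C-SSRS can prevent at most 1 of 18 doses, and none if it follows the Day 19 injection. For extenders, Day 19 is useful because it precedes the 2.4 mg step and leaves 12 or 13 doses stoppable, but the Day 31 check has the same weakness.

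This concerns scheduled, structured assessment. It does not show that ideation would go unnoticed, and no claim is made about how many events would be caught. The plan breaks no requirement of its own. The change is worth making because it is cheap, the protocol itself names the risk and sets the stop rule, and the drug is new to this population. The counts rest only on the dosing and visit schedule.

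**What to change.** Give the C-SSRS on Days 8 and 14 to all participants and on Day 26 to extenders, before that day's dose where possible. If the visit falls after the morning dose, either do it the evening before or accept it after the dose, which still leaves 11 and 5 of 18 doses stoppable (5 of 30 on Day 26). State which version is used after baseline, and have it cover the whole period since the previous assessment on every occasion, including Days 19 and 31, so that ideation which has resolved is also recorded. Update the activity lists in 7.2.3, 7.2.4 and 7.2.8 and both schedule tables. A cross-reference from 3.3.1 and 18.7 to the rule in 7.2 would be tidy but is optional.

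The cost is 100 to 150 administrations in total. Assuming 5 to 10 minutes each (not a figure from the documents), that is 10 to 20 minutes per 3-dose participant and 15 to 30 per extender. The visit days, trained staff and referral pathway already exist; an evening-before slot would be a new contact. More detection may bring a few more clinician evaluations or discontinuations, in a trial that already allows for 20% attrition. Endpoints, sample size and analysis do not change.
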